#### Secondary Outcome

Secondary outcome is weight development and "Adult Social Care Outcomes Toolkit" (ASCOT) questionnaire (27).

#### All outcome measures

Data are collected at baseline and 6 months (m). The starting point is the same measurements as described in sub-study 1, combined with feasibility in practice.

The data analysis takes into account that not all participants are included in all measurements.

Tabel 1: Data collection in sub study 2

Variable	Method	Baseline	6 m
Age and sex	Journal data	x	
Weight	Calibrated standard weight as part of routinely weighing, Journal data	x	x
Weight, fat%, fat mass (kg), muscle mass (kg), bone mass (kg), BMI, total body water (TBW), TBW%, intracellular water and extracellular water	BIA	x	x
Calf circumference	Measured by non-elastic plastic tape		
Height	Journal data	x	
Height measured	Measured standing or lying	x	
Chronic disease, diagnosis and number	Journal data	x	
Muscle function	30 s CST , gait speed and HGS	x	x
Nutritional risk	EVS	x	x
Quality of Life	ASCOT questionnaire	x	x

#### **c. Deviations from standard care**

Control group include three nursing homes and participant will follow standard care. The interventions group including three nursing homes will implement the intervention developed on

the basis of new knowledge from sub-study 1, previous studies, practical experiences, the participant's experiences and wishes as well as the staff's experiences and wishes.

#### **4. Statistical analysis**

The analysis follow the intention-to-treat principle and thereby including all data after randomization, regardless of non-compliance or lack of results.

The effect of measures and intervention is assessed using covariance analysis (ANCOVA) adjusted for baseline and potential confounders. Kaplan-Meier analysis and parametric or non-parametric regression and correlation analyzes are used to assess data in a timeline perspective with multiple measurements of physical functioning, weight, muscle mass, and care-related quality of life.

Data on recruitment and participants' feasibility and compliance in relation to intervention will be assessed by descriptive and comparative analyzes.

A statistical software program for scientific research e.g. SPSS or R will be used for statistical analyzes.

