### 3. Methods

#### a. Study design and methods

This pragmatic feasibility cluster randomized controlled intervention study will be performed at six nursing homes in Odsherred City. Participants and care staff from nursing homes in Odsherred City will contribute to the design of this study protocol.

The research group include participants experience from sub study 1. Moreover, the participant's experiences are central during the feasibility state.

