#### Sample size calculation:

Initially the power calculation is performed by the individual randomization, calculated on the basis of the 30 secound chair stand test. The starting point is six nursing homes is involved in the study. Approximately 40-50 residents are living in each location and assumable half of them are Ow/O and wants to participate in the project. (n=20). A desired detectable change of 1.3 (39), a P-value <0.05 and a power of 80%. The study has two arms (control and intervention) and the standardized difference in the nursing center incl. intra cluster correlation, SD diff, nursing center = 0.42.  $SD(\text{diff.}, \text{nursing center}) = (SD(\text{diff.}, \text{person}))/\sqrt{n}$ , SD diff, person  $\approx 1.87$  If SD is 1.87 or less, the power will be at least 80% or greater. If there are more than 20 people per. care center power will increase and if there are fewer than 20 people power will decrease. After sub study 1 a more accurate number can be provide, also knowing what is feasible in sub study 2.

Approximately 100 participants will be included and cluster randomized to either 6 month of nutritional and physical intervention or 6 month of usual care (control). A simple random sample without replacement will be selected by a non-project group member using the lottery method. Effects from the intervention will be examined by mixed methods that include both quantitative and qualitative data, as well as action research that focuses on creating development and change in collaboration with participants and care staff at the nursing homes.

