#### Intervention

The intervention is developed with a focus on nutritional needs and physical activities.

In follow-up, the PDSA model (25,26) is used to redefine issues and relevant actions together with care staff, the nursing home management and participants. The intervention will be developed on

the basis of new knowledge from sub-study 1, previous studies, practical experiences, the participant's experiences and wishes as well as the staff's experiences and wishes. Together they will be form an implementation catalog, from here, the nursing homes can select a relevant number of components, which will be tested and implemented in practice. An example could be that the general offer of diet type at the nursing home is changed to the diet type "normal" diet for older adult with a high protein content instead of enriched diet type for malnourished older adults (4). Whether the participants are at nutritional risk is assessed by Ernæringsvurderingsskemaet (EVS), and the participants who need a enriched diet or special diet forms such dysphagia diet (4), is of course offered / continues these diets . However, it may be that some participants can achieve / maintain a better physical function with a normal diet.

The implementation duration is 6 months and the PDSA model (25,26) repeated at two-month intervals to strengthen and qualify the intervention. The PDSA model is known to the city's staff in advance, and is additionally used in connection to continuing education. In addition, every day physical activities that contributes to maintaining / improving physical functional is included, based on the potentials that are uncovered in sub-study 1.

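### Six nursing homes are randomised, but the effect analysis is an ANCOVA that takes no account of home, so the 5% error rate fails as soon as residents of a home resemble each other

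*Protocol*

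**What the plan says.** Section 3a sets the design: "This pragmatic feasibility cluster randomized controlled intervention study will be performed at six nursing homes in Odsherred City". Section 3c gives the allocation: "Control group include three nursing homes and participant will follow standard care", and for the other arm "The interventions group including three nursing homes will implement the intervention developed on" knowledge from sub-study 1 and other sources. So the home is the unit of randomisation, three per arm.

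The sample size calculation uses the 30-second chair stand test. It sets "A desired detectable change of 1.3 (39), a P-value <0.05 and a power of 80"%, takes 20 residents per home, and works with a home-level SD: "the standardized difference in the nursing center incl. intra cluster correlation, SD diff, nursing center = 0.42". It converts this to a person-level SD and adds "If SD is 1.87 or less, the power will be at least 80% or greater". The planned total is about 100 residents.

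Section 4 applies intention to treat to all data after randomisation and names the effect analysis: "The effect of measures and intervention is assessed using covariance analysis (ANCOVA) adjusted for baseline and potential confounders". It mentions no random effect for home, home-level summary, cluster-robust variance or reduced degrees of freedom. Neither clustering nor the nursing home appears anywhere in that section.

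**The concern.** Residents of one home share staff, kitchen, routines and case mix, so their outcomes tend to be alike. When whole homes are allocated, the arm comparison carries this home-to-home variation, and only six homes are available to measure it. A model that counts residents as independent leaves that variation out of the standard error and uses about 97 degrees of freedom where the design supplies 4.

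Adjusting for confounders does not help. As an ordinary covariate, home is completely aliased with arm, and the intervention effect can then no longer be estimated.

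Every between-arm p-value and interval for the primary and secondary outcomes is affected, and the error runs toward false positives. Ordinary differences between homes could be reported as an effect of the intervention. The protocol plans a publication on effects and an implementation catalogue for use in other Danish cities, so a spurious effect would travel.

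**Working it through.** **Inputs from the protocol.** Six homes, three per arm (sections 3a and 3c). Difference 1.3 stands, alpha 0.05, power 80%, home-level SD 0.42, person-level SD 1.87, 20 residents per home, about 100 residents in total (sample size calculation). Sidedness is not stated; two-sided reproduces the figure.

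**Assumption.** The protocol gives no ICC value. I used 0 to 0.10, as the residual ICC after baseline adjustment, and took 1.87 as the person-level SD of the analysed outcome.

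**Step 1: reproduce the stated power.** Two-sample t-test on home means, 3 v 3, df = 6 − 2 = 4:

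- SE = 0.42 × √(2/3) = 0.343
- noncentrality = 1.3 / 0.343 = 3.79, critical value t(0.975; 4) = 2.776
- power = 80.6% (80.9% with 1.87/√20 = 0.418); the SD that gives exactly 80% is 0.423

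Alternatives do not reproduce it: one-sided 92.4%; three matched pairs 76.6%; normal approximation on home means 96.6%; residents as independent, 60 per arm with SD 1.87, 96.8%. The trial was therefore sized with the home as the unit of analysis.

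**Step 2: error rate of the ANCOVA without home.** With m = 100/6 = 16.7 residents per home, design effect DE = 1 + (m − 1) × ICC. The true SE is √DE times the one reported, so the true two-sided error is about 2 × [1 − Φ(1.96/√DE)]. Example at ICC 0.05: DE = 1 + 15.67 × 0.05 = 1.78, √DE = 1.34, error = 14.2%.

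**Step 3: interval widths.** The unclustered model gives SE = 1.87 × √(2/50) = 0.374 and a half-width of about 1.98 × 0.374 = 0.74 stands. For homes, SD of a home mean = 1.87 × √[(1 − ICC)/m + ICC], and half-width = 2.776 × that SD × √(2/3).

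| ICC | DE | √DE | Type I error, formula | Type I error, simulated | Coverage of nominal 95% interval | Home-mean SD | 4-df half-width |
|---|---|---|---|---|---|---|---|
| 0 | 1.00 | 1.00 | 5.0% | 4.3% | 95% | 0.458 | 1.04 |
| 0.01 | 1.16 | 1.08 | 6.8% | 6.7% | 93% | 0.493 | 1.12 |
| 0.02 | 1.31 | 1.15 | 8.7% | 8.7% | 91% | 0.525 | 1.19 |
| 0.05 | 1.78 | 1.34 | 14.2% | 13.9% | 86% | 0.612 | 1.39 |
| 0.10 | 2.57 | 1.60 | 22.1% | 22.7% | 78% | 0.734 | 1.66 |

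The simulated column comes from 10,000 null trials per setting with 100 residents in six homes, analysed by ANCOVA on arm and baseline. With 20 per home the simulated error is 4.8%, 6.9%, 9.5%, 16.3% and 25.4%.

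**Step 4: does a home-level analysis hold the level?** In the same simulations, a t-test on baseline-adjusted home means with 4 df rejected in 4.6% to 5.5% of null trials across all ICCs and both trial sizes.

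**The case against.** Section 4 does not say the ANCOVA is at resident level. An ANCOVA can be run on home means or with home as a random factor, and the sample size calculation shows that the authors knew about clustering. Random effects and degrees of freedom are often left to an analysis plan, which may exist. This does not remove the point. Including all data after randomisation and adjusting for baseline and confounders reads most naturally as a resident-level model, and with six home means several covariates would use up the residual degrees of freedom. The protocol names a model, and that model does not match its own design and power calculation.

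Three qualifications stand:

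- The error-rate inflation needs an ICC above zero. At ICC 0 the test holds its level, and at 0.01 the excess is modest. The larger figures rest on assumed ICCs, although the protocol itself refers to intra-cluster correlation.
- Part of the widening comes from the 4 degrees of freedom, not from a larger standard error. At ICC 0 the half-width already rises from 0.74 to 1.04. That accounts for 0.30 of the 0.38 increase at ICC 0.01, and 0.30 of 0.65 at ICC 0.05.
- The choice of components ("from here, the nursing homes can select a relevant number of components") concerns delivery of the intervention, and control homes follow standard care. If no component works, differing choices create no spread between homes, so they do not cause false positives. They do add between-home variation when components differ in effect, which then harms interval coverage.

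**Conclusion.** The point holds. The analysis named in section 4 does not respect the unit of randomisation and does not match the calculation that sized the trial. At about 100 residents, its nominal 5% test has a true error of about 7%, 14% and 22% at ICC 0.01, 0.05 and 0.10, and its 95% intervals cover about 93%, 86% and 78%. At an ICC of 0.05 or more, the valid half-width (1.39 stands or wider) exceeds the 1.3 stands the trial aims to detect, which the planned analysis would conceal.

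These sizes depend on the assumed ICC range, a person-level SD of 1.87, near-equal homes and the resident-level reading of section 4. The mismatch between design, sample size and analysis does not depend on the ICC. It should be corrected before any between-arm analysis.

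**What to change.** Replace the ANCOVA sentence in section 4 with a home-level analysis. Recommended: regress each resident's 6-month value on the baseline value without an arm term, average the residuals by home, and compare the six home means with a two-sided t-test on 4 degrees of freedom. This matches the protocol's power calculation and held the 5% level in simulation. Further resident-level covariates may enter the first step if named in advance; home-level covariates should not, because they consume the 4 degrees of freedom.

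A linear mixed model with arm, baseline and a random home intercept, using Kenward-Roger or Satterthwaite degrees of freedom, is a possible alternative. I did not simulate it. With six homes the home variance can be estimated as zero, so its error rate should be checked first. Uncorrected robust standard errors or GEE are unreliable with six clusters. A home-level permutation test cannot reach 5%: three versus three gives 20 allocations, so the smallest two-sided p is 2/20 = 0.10. Report the ICC with each result.

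The edit is one sentence and needs no extra data. The cost is wider intervals and a power statement that must be revisited: with SD 1.87 and about 100 residents, home-level power is 73.9% at ICC 0 and 50.7% at ICC 0.05, not 80%.

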#### **5. Study population**

Participants are recruited from nursing homes in Odsherred City in Region Zealand, Denmark.

##### **a. Inclusion criteria:**

- Living at the nursing homes in Odsherred City
- Informed consent form signed after receiving oral and written information
- Read, speak and understand Danish

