## **STUDY Protocol Sub-study 2: Interventions focusing on nutrition and physical activities for overweight and obese older adults in nursing homes "IFEBO" (A feasibility study)**

**Authors:** [name], [name], [name], [name] and [name]

- 1. Title for the project:** Interventions focusing on nutrition and physical activities for overweight and obese older adults in nursing homes "IFEBO"
- 2. Purpose:** The overall purpose is to investigate how muscle function and care-related quality of life can be maintained or improved through nutrition and physical activity interventions in older adults in nursing homes. Older adults with the combination of both overweight and T2D have a special focus in the sub-study, as the two conditions together increased the demands on the nutritional intervention.
  - a. Specific objectives:**
    - What components of existing practice should be included in interventions focusing on nutrition and physical activities?
    - What interventions are feasible in practice?
    - Does the screening model identify the older adults in need of a nutrition and physical activity intervention?

The project's hypothesis is that the older adults with Ow/O may be malnourished and may benefit from interventions that combine nutrition and physical activities.

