In addition, the studies show that there is no difference between whether the nutrition intervention applies weight loss or weight maintenance interventions (10–20,22,23), but that the intervention itself has an effect, even when the weight is maintained.

However, the above literature review has confirmed that there are older people with Ow/O, especially those with both low physical function and chronic disease, who may benefit from a nutritional intervention, which has led to a proposed screening model (24). The characterization according to the screening model will be performed in sub-study 1, and furthermore adapted to be easy-to-use in a community health care setting.

In sub study 2, on the basis of the screening model (sub study 1), the project, in co-creation with the older adults, the care staff and the project participants, develop and test nutritional interventions that can improve muscle function and quality of life of the target group.

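### The entry criteria contain no overweight/obesity (Ow/O) or other target-group condition, yet the hypothesis, the sample size and the planned conclusions concern residents with Ow/O, and the protocol does not say whether open entry is intended

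*Protocol*

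**What the plan says.** **Who may enter.** Section 5a lists three conditions: "Living at the nursing homes in Odsherred City", signed consent, and command of Danish. Section 5b has one exclusion, terminal illness. There is no BMI threshold, Ow/O definition or screening-model result. Section 12 addresses recruitment to the homes' residents in general. Section 4 applies intention-to-treat to all data after randomisation and names no Ow/O set.

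**Whom the trial is about.**
- The title is "Interventions focusing on nutrition and physical activities for overweight and obese older adults in nursing homes".
- The hypothesis in section 2a is that "the older adults with Ow/O may be malnourished and may benefit from interventions that combine nutrition and physical activities".
- The sample size in section 3a takes 40-50 residents per home and says "assumable half of them are Ow/O and wants to participate in the project", giving n=20.
- Section 13 plans strategies for dealing with Ow/O, and section 14b states the benefit for older adults with Ow/O.

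**Narrower target-group wording.** Section 2b describes the project's target group as having both reduced muscle function and chronic disease, and bases sub-study 2 on the screening model. Section 2 gives special focus to overweight combined with type 2 diabetes.

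**Wording that fits broad entry.** The overall purpose is framed as "through nutrition and physical activity interventions in older adults in nursing homes". The third objective asks "Does the screening model identify the older adults in need of a nutrition and physical activity intervention". Section 3b gives a home-wide change of diet type as an example of an intervention.

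**The concern.** Site staff will recruit by sections 5 and 12, not by the title. Followed exactly, those sections enrol residents with and without Ow/O, and the analysis pools them. The resulting estimate answers a question about consenting residents at large, whereas the hypothesis, the power statement and the planned strategies need an answer for residents with Ow/O.

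If residents without Ow/O respond differently, the pooled result cannot be read for the Ow/O group. If the Ow/O group is separated out only once results are known, that choice is open to bias.

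**Working it through.** **1. Comparing the sections.** Sections 5a and 5b admit residents regardless of Ow/O, and section 4 analyses whoever was admitted. Section 3a counts only residents with Ow/O who wish to take part. Sections 13 and 14b draw conclusions only for Ow/O. No section states that residents without Ow/O are enrolled on purpose, or how their data bear on the Ow/O conclusions. The third objective might explain open entry, but section 2b says "The characterization according to the screening model will be performed in sub-study 1", so it does not clearly do so for this sub-study.

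**2. Inputs, all from section 3a unless noted.** Detectable change 1.3 on the 30-second chair stand test; significance level 0.05 (two-sided assumed); home-level SD 0.42 at 20 per home; six homes, three per arm (section 3c); "Approximately 100 participants will be included and cluster randomized".

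**3. Reproducing the stated power.** Two-sided t-test on 3 versus 3 home means, 4 degrees of freedom, critical value 2.776, noncentrality = delta / (SD × √(2/3)).
- 1.3 / (0.42 × 0.8165) = 3.79, power 80.6%. This matches the stated 80%, which therefore refers to 20 participants with Ow/O per home.

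**4. Illustrations under assumed mixes.** The protocol's formula, person SD / √n, gives home SD = 0.42 × √(20/n).

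Only participants with Ow/O analysed, delta 1.3:

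| Assumed enrolment | Ow/O per home | Home SD | Noncentrality | Power |
|---|---|---|---|---|
| Others enrol in addition to 20 with Ow/O per home | 20 | 0.420 | 3.79 | 80.6% |
| Half of 100 participants have Ow/O | 50/6 = 8.33 | 0.651 | 2.45 | 46.2% |

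All 100 analysed (100/6 = 16.67 per home, home SD 0.460), half without Ow/O, same SD in both groups:

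| Response of residents without Ow/O | Mean effect | Noncentrality | Power |
|---|---|---|---|
| None | 0.5 × 1.3 = 0.65 | 1.73 | 26.7% |
| Half the effect | 0.75 × 1.3 = 0.975 | 2.60 | 50.5% |
| The full effect | 1.3 | 3.46 | 73.6% |

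The last row involves no dilution. Its shortfall from 80.6% comes only from having 16.67 rather than 20 participants per home.

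**5. Sensitivity to the SD formula.** The 0.42 is said to include the intra-cluster correlation, so shrinking all of it with √n is pessimistic below 20 per home. If half of 0.42² = 0.1764 is taken as between-home variance (an assumption), then at 8.33 per home SD = √(0.0882 + 0.0882 × 20/8.33) = 0.548, and the 46.2% becomes 59.4%.

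**The case against.** The strongest reply is that open entry is a defensible choice for a pragmatic feasibility study. The purpose is worded for nursing-home residents generally, the screening-model objective may need residents of all kinds, and a diet change across a whole home reaches everyone. This stands as a reason not to call open entry a mistake. It does not remove the inconsistency, because the protocol never states the choice and sizes the trial for a different group.

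A second reply is that a statistical analysis plan may define an Ow/O set. It may, but entry criteria belong to the protocol, and the disagreement lies within this document.

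Three stronger readings are tempting and are not supported:
- A reader might infer that section 4 is a second, independent error. It only states intention-to-treat and takes its population from section 5.
- A reader might infer that open entry costs the trial its power. The low figures require residents without Ow/O to displace others within a fixed 100. Section 3a expects about 20 willing residents with Ow/O per home. If others join in addition to these, an Ow/O-only analysis keeps 80.6%. Section 3a also calls its numbers provisional until sub-study 1 reports.
- A reader might infer that a BMI criterion alone would settle the matter. Section 2b describes a narrower target group, so that wording has to be reconciled too.

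**Conclusion.** The point holds as an unreconciled mismatch. The protocol's entry rule, carried into its analysis, gives an estimate for a mixed population, while the hypothesis, the sample size and the conclusions concern Ow/O. It should be resolved before data are seen, because it decides who is enrolled and whom the main result describes.

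The mismatch rests on the text alone. Its numerical cost cannot be fixed from the document: the share of participants without Ow/O and their response are not given. Under the assumed mixes, power runs from 80.6% (no loss) to about 46% for an Ow/O-only analysis, and from 27% to 74% when all 100 are analysed. The loss due to mixing could be nil.

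The difference between 20 × 6 = 120 and the roughly 100 planned would exist even if every participant had Ow/O. It is a separate matter and adds no weight here.

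**What to change.** Choose one of two routes and make sections 2, 3a, 4, 5 and 12 agree with it.

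**(a) Restrict entry.** Add an Ow/O criterion to section 5a with a threshold set by the sponsor, and reconcile it with the target-group and screening-model wording in section 2b. Apply it identically in both arms and in a way that knowledge of a home's allocation cannot influence; this matters because section 3b foresees ongoing inclusion. State when the check takes place relative to consent. Cost: residents without Ow/O are excluded, and the screening-model question may be limited, so the protocol should say where the third objective is answered.

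**(b) Keep entry open.** State that all residents may enrol and why. Prespecify participants with Ow/O at baseline as the set for the Ow/O hypothesis, report the others separately, and tie the 80% power to the number of participants with Ow/O expected. Cost: power for the Ow/O set may be lower.

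Either route is mostly a change of text. Weight, height and BMI are already baseline items in Table 1, so no new measurement is needed.

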#### Primary outcome

Primary outcome is sustained or improved muscle function (30 - second chair stand test (30 s CST), gait speed (10 meters) and hand grip strength (HGS))

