## **12. Recruitment of subjects and informed consent**

Recruitment of project participants takes place from Odsherred city's 6 nursing homes. The first step in recruitment takes place by principal investigator orally and in writing informing the nursing homes, care staff, relatives, nursing home councils and the residents of the nursing homes about the project's purpose, content and course. Posters are posted telling about the project. In the next step, (oral information) the principal investigator, the care staff and relatives talk to the residents.

Participant information (written information) is provided for both sub-studies as well as the leaflets "Subjects' rights in a health science research project", and "Before you decide - to be in health science experiments". The written information contains a description of the project, its purpose, method and possible consequences associated with the participants' participation. Participation in the project is voluntary, and the participants have the opportunity, without further justification, to interrupt the collaboration and their participation in the project. In the third step, the residents then have 24 hours to decide whether they want to participate in the project and sign a declaration of consent. During the project period, the participants can obtain further information about the project from the principal investigator. Collection, storage and processing of empirical data is done with the Danish Data Protection Agency's instructions for handling confidential information in research work of an empirical nature.

Participants have the opportunity to withdraw consent at any time during the project. If there are measurements, eg performance tests, which the participants do not want to participate in, available data is collected from the journaling system (CURA) without participation in all measurements.

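### The stated 80% power needs 20 chair-stand values per home, but the 20 counts residents willing to join, and some of those may supply no value.

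*Protocol*

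**What the plan says.** **Who enters.** Protocol section 5a requires "Living at the nursing homes in Odsherred City", signed consent and command of Danish. Section 5b excludes only the terminally ill. Neither mentions being able or willing to do a physical test.

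**Who stays.** Section 12 says: "If there are measurements, eg performance tests, which the participants do not want to participate in, available data is collected from the journaling system". Such a resident remains a participant. Under All outcome measures the protocol adds: "The data analysis takes into account that not all participants are included in all measurements". It gives no rule for doing so. Table 1 there allows height to be "Measured standing or lying", so residents who are not measured upright are foreseen.

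**What n means.** The Sample size calculation (section 3a) takes homes of about 40 to 50 residents, supposes that half are overweight or obese and want to join, and sets n = 20 per home. Power is based on the 30-second chair stand: a change of 1.3, significance level 0.05, 80% power, SD 0.42 for a home and 1.87 for a person. It notes that "if there are fewer than 20 people power will decrease" and that a more accurate number can follow sub-study 1. The same section expects about 100 participants in total.

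**Outcome and analysis.** "Primary outcome is sustained or improved muscle function", measured by chair stand, 10 m gait speed and hand grip strength. Section 4 states: "The effect of measures and intervention is assessed using covariance analysis (ANCOVA) adjusted for baseline and potential confounders".

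**The concern.** The sample size calculation treats each of the 20 as a chair-stand value. The recruitment rules produce a different quantity: people who agree to be in the project, some of whom are expressly allowed to skip the test on which power is based. Nothing in the protocol links the two counts.

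If the gap is material, the trial can reach its enrolment target and still have fewer primary values than its power statement assumes. A null chair-stand result would then be read against 80% power that the trial did not have.

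A related gap concerns residents who physically cannot rise. The protocol does not say whether inability is a score of 0 or a missing value. If it is treated as missing at 6 months, a resident who loses the ability to stand drops out of the comparison, although that loss is exactly what the outcome should register.

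**Working it through.** **Inputs** (Protocol, Sample size calculation; section 3c for the three-against-three split):
- difference 1.3 stands; significance level 0.05, taken as two-sided because that reproduces the stated power
- person SD 1.87; home SD = 1.87/√n
- three homes per arm
- n = 20 per home, or about 100 in total, which is 100/6 = 16.7 per home

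**Method.** Two-sample t-test on home means, 3 against 3, with 4 degrees of freedom. The noncentrality is 1.3 / (home SD × √(2/3)), and power comes from the noncentral t distribution. The protocol does not name its test; this one was chosen because it returns the protocol's figure.

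**Step 1: reproduce 80%.** The home SD is 1.87/√20 = 0.418, which the protocol rounds to 0.42. With 0.42 the noncentrality is 1.3 / (0.42 × 0.816) = 3.79 and power is 80.6%. With 0.418 power is 80.9%. Two alternatives do not fit: a normal approximation gives 96.6% and a one-sided t-test 92.4%.

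**Step 2: vary the share with a value.** The protocol gives no such share, so the first column is an assumption. Each row uses 1.87/√(number with a value).

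| Share with a chair-stand value | Power, 20 enrolled per home | Power, 16.7 enrolled per home |
|---|---|---|
| 100% | 80.9% (20 values) | 73.9% |
| 90% | 77.0% (18) | 69.7% |
| 80% | 72.3% (16) | 64.9% |
| 70% | 66.9% (14) | 59.4% |
| 60% | 60.5% (12) | 53.3% |

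**Step 3: the total.** Twenty in each of six homes is 120, not about 100. At 16.7 per home power is 73.9% before anyone goes untested.

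**Step 4: sensitivity to between-home variance.** Dividing the person SD by √n leaves no variance between homes. With an assumed intra-cluster correlation of 0.05, the home SD is 1.87 × √(0.05 + 0.95/n). Power is then 54% at n = 20, and 50%, 47% and 44% at n = 16, 14 and 12. The level is lower throughout, and the loss from 20 to 12 values is about 10 points (54 − 44) instead of about 20 (80.9 − 60.5).

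**The case against.** **The design is meant to be broad.** This is a pragmatic feasibility study, and open entry suits it. It also plans to describe recruitment, feasibility and compliance. That stands, and it is a reason not to add a functional entry criterion. It does not alter what the 20 must mean for the stated power to hold.

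**The protocol already hedges.** It says that power falls below 20 per home and that sub-study 1 will sharpen the number. It also presents 1.87 as a ceiling on the SD, so a smaller SD would offset some loss. This is partly right, but the promised update is not tied to a count of residents with test values.

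**The SAP may cover missing data.** It may. Handling of missing values does not change the definition of n behind the protocol's power statement.

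**Stronger readings that the protocol does not support.** A reader might infer that a resident who scores 0 at baseline automatically counts as sustained. The protocol has no responder rule: it plans ANCOVA adjusted for baseline. It does not say that non-performers score 0, the outcome also includes grip strength, which needs no standing, and a resident at 0 can still improve. A reader might also conclude that such residents dilute the 1.3-stand effect by a set fraction. That assumes both zero scoring and no response in any of them, and neither is stated. The lying option for height shows only how height is taken, not a chair-stand score.

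**Conclusion.** The mismatch is real. The protocol's 80% power requires 20 chair-stand values per home, while its 20 is a count of residents willing to take part, and its own rules admit and retain people who give no value.

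The size of the loss cannot be fixed from the protocol. On its own SD formula, if 20%, 30% or 40% of 20 enrolled per home have no value, power is about 72%, 67% or 61%. At the stated total of about 100 it is about 74% with everyone tested. These figures assume a person SD of 1.87, no between-home variance and no further loss by 6 months. Allowing for between-home variance lowers all of them and makes the loss from untested residents smaller in points.

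This is a correction to the sample size statement and a scoring rule, not a case for restricting entry.

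**What to change.** In the Sample size calculation, define the number per home as residents with a baseline chair-stand value. Restate the power for the number expected, using the testable share seen in sub-study 1 and an enrolment total that agrees with it. No increase in enrolment is required.

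Under the primary outcome, add a scoring rule. Physical inability to rise scores 0 at both visits, so that loss of function by 6 months counts as decline; refusal is missing. Report by arm how many residents were untested, and how many scored 0, at baseline.

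Keep enrolment broad and keep baseline zeros in the analysis. Limiting the primary set to residents who complete at least one rise would remove those who might improve from 0. It would also sit badly with the intention-to-treat statement in section 4. With whole homes randomised and inclusion ongoing, it would be hard to apply such a limit before allocation is known.

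The cost is a few sentences and a stated power that is less favourable than 80%.
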